### **6.4 Postoperative Management**

In the post-anesthesia care unit (PACU), patients are monitored for 2 hours. NRS scores at rest and during movement, mean arterial pressure, and heart rate are recorded on arrival. On the ward, patients receive paracetamol 500 mg IV every 6 hours. Rescue analgesia consists of morphine 0.05 mg/kg IV bolus when NRS  $\geq 4$  at rest or during movement, with a maximum dose of 0.3 mg/kg in 24 hours. Ondansetron 0.1 mg/kg IV is administered for moderate or severe postoperative nausea/vomiting.

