## **7. Outcomes and Assessments**

### **7.1 Primary Outcome**

The primary outcome is total morphine consumption (mg) in the first 24 postoperative hours, calculated as the cumulative dose of intravenous morphine administered in the PACU and on the ward up to 24 hours after surgery.

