### **7.2 Secondary Outcomes**

To compare intraoperative fentanyl consumption between the three groups.

To compare time to first rescue analgesia postoperatively.

To compare Numeric Pain Rating Scale (NRS) scores at rest and during passive 90° hip flexion at predefined postoperative time points (30 min, 2, 4, 6, 8, 12, 18, and 24 hours).

To assess block failure rate, defined as the requirement for more than one rescue morphine dose in the first postoperative hour.

To compare motor recovery (manual muscle test for quadriceps and iliopsoas, and active hip flexion range of motion) over the first 24 hours.

To compare time to first ambulation and length of hospital stay.

To compare intraoperative hemodynamic profiles (heart rate and mean arterial pressure).

To compare the incidence of block-related complications and morphine-related adverse events (e.g., nausea/vomiting, respiratory depression, hypotension, falls).

To compare block performance time and surgical duration between groups.

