## **8. Sample Size Determination**

The planned analysis for the primary outcome is a three-arm comparison of 24-hour opioid consumption. Based on retrospective data reporting 24-hour hydromorphone consumption of  $4.5 \pm 2.9$  mg after PENG block, a conservative standardized effect size of 0.35 was assumed. With  $\alpha = 0.05$  (two-tailed), power of 80%, and three groups, the required sample size was 81 patients. Allowing for approximately 15% attrition, the final target sample size was 93 participants (31 per group).

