### **11.3 Handling of Missing Data**

The study is expected to have minimal missing data due to the short follow-up period. If missing data occur, the primary approach will be complete-case analysis. Reasons for missingness will be documented. No formal imputation strategy is planned.

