## **11.6 Secondary Outcome Analyses**

Total intraoperative fentanyl dose and other continuous secondary outcomes (such as time to first rescue morphine, time to ambulation, length of hospital stay, block performance time, and surgical duration) will be analyzed using one-way ANOVA for normally distributed data or Kruskal–Wallis test for skewed data, with appropriate pairwise post-hoc tests. NRS pain scores at rest and during movement and motor recovery scores will be analyzed at each time point using Kruskal–Wallis tests with Bonferroni-adjusted Mann–Whitney comparisons. Exploratory repeated-measures analyses (e.g., mixed-effects models) may be used to evaluate time-by-group interactions when assumptions are satisfied. Categorical outcomes, such as adverse event incidence and block failure rates, will be compared using chi-square or Fisher’s exact tests as appropriate.

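### Time to first rescue morphine is analysed as an ordinary continuous variable, with no rule for patients who need no rescue within 24 hours

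*Combined protocol and SAP*

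**What the plan says.** Section 7.2 of the combined protocol and SAP lists the outcome as "To compare time to first rescue analgesia postoperatively", and Section 2.2 has it among the secondary objectives. Neither gives a start point, a cut-off or a rule for a patient without the event. By contrast, Section 6.5 defines time to first walk from the end of surgery.

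Rescue is conditional. Section 6.4 begins "Rescue analgesia consists of morphine 0.05 mg/kg IV bolus when NRS" and goes on to set a threshold on the pain score. Morphine is counted over a fixed window: the primary outcome in Section 7.1 is the "cumulative dose of intravenous morphine administered in the PACU and on the ward up to 24 hours after surgery".

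For analysis, Section 11.6 groups this outcome with "other continuous secondary outcomes (such as time to first rescue morphine, time to ambulation, length of hospital stay, block performance time, and surgical duration"), all of which "will be analyzed using one-way ANOVA for normally distributed data or Kruskal–Wallis test for skewed data". On absent values, Section 11.3 says "If missing data occur, the primary approach will be complete-case analysis" and "No formal imputation strategy is planned". Censoring, Kaplan–Meier, log-rank and Cox methods appear nowhere in the document.

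**The concern.** A patient who never reaches the trigger has no observed time. All that is known is that the time exceeds the observation window, so it is right-censored. ANOVA and Kruskal–Wallis need a number for every patient analysed, and the plan leaves two ways of supplying one.

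- **Drop these patients.** This is the literal reading of Section 11.3, although the plan does not actually call them missing. It selects on a post-randomisation outcome that the blocks are meant to change. The same patients have a valid 0 mg primary outcome and so belong to the Full Analysis Set of Section 11.2.
- **Enter 24 hours.** This keeps them, but it understates mean times and loses some power.

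If the blocks work, rescue-free patients will be more common in the block arms. Dropping them then pulls the comparison towards no difference and can reverse the order of PENG and AQLB, a direct comparison that Section 1 names as a purpose of the trial. With no rule written down, the choice could be made after the data are seen.

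**Working it through.** **Inputs from the document.** Three arms, 1:1:1 (Section 3); 31 per arm, or 27 evaluable (Section 8); two-sided 0.05 (Section 11.1); a 24-hour morphine window (Section 7.1). The plan attaches no figure to this outcome. The sample size behind the arm sizes is sound enough: noncentral-F power for three groups at N = 81 and f = 0.35 is 79.6%, against the stated 80%.

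**How many patients could be rescue-free?** The document gives no rate. The nearest guide is in Section 8 ("Based on retrospective data reporting 24-hour hydromorphone consumption of" 4.5 ± 2.9 mg), which is retrospective and concerns another opioid. If a fraction p takes nothing, the variance is smallest when all others take the same dose, which gives p/(1 − p) ≤ (SD/mean)².

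- r = (2.9/4.5)² = 0.415, so p ≤ 0.415/1.415 = 0.293, a ceiling of 29%.
- A normal approximation gives Φ(−4.5/2.9) = 0.060, or 6%.

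**Simulation.** 2,000 trials per scenario, 31 per arm, Weibull times with shape 1.2. In the first three rows each arm has one Weibull curve censored at 24 h, so the rescue-free rate is exp(−ln 2 × (24/median)^1.2): 7.5% at a median of 8 h, 13.8% at 10 h and 20.3% at 12 h. The two equal-times rows add a never-rescued fraction to times with a nominal median of 6 h in every arm. All medians and rates are assumptions. KW is Kruskal–Wallis; arms are in the order PENG/AQLB/Control; entries are power in %.

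| Scenario | Rescue-free (%) | KW, rescued only | KW, 24 h entered | ANOVA, 24 h entered | Log-rank |
|---|---|---|---|---|---|
| Medians 8/8/4 h | 7.5/7.5/0.3 | 68–69 | 82–84 | 89 | 92 |
| Medians 10/8/5 h | 14/7.5/1 | 48 | 72 | 80 | 85 |
| Medians 12/8/6 h | 20/7.5/3 | 33 | 69 | 76 | 80 |
| Equal times among rescued, at the ceiling | 29/15/0 | 4–5 | 38–42 | 55–62 | 67–77 |
| Equal times among rescued | 6/6/0 | ≤12 | ≤12 | ≤12 | ≤12 |
| 8/8/4 h, nobody rescue-free | 0/0/0 | about 72 | about 72 | – | 79 |

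The last row shows that part of the log-rank advantage comes from the proportional hazards built into the model, not from its handling of censoring.

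**A second model.** Exponential times, 27 per arm, 3,000 trials, censored at 24 h. The hazard is −ln(p)/24, where p is the rescue-free share (order here: Control/block/block).

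| Rescue-free (%) | KW, rescued only | KW, 24 h entered | Log-rank |
|---|---|---|---|
| 2/10/10 | 23 | 38 | 49 |
| 2/20/20 | 47 | 81 | 91 |
| 2/30/30 | 59 | 98 | 99 |
| 10/30/30 | 15 | 52 | 61 |

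At 20% rescue-free the true median is 24 × ln 2/(−ln 0.20) = 10.3 h; among rescued patients only, it averages about 7.8 h. With identical arms all three methods reject in 4.4–6.1% of trials. The problem is therefore lost power and distorted estimates, not false positives.

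**Reversal of order.** Take times truncated at 24 h with nominal medians of 5.5 h (PENG) and 6 h (AQLB), and 20% v 5% never rescued. The rescued-only median is the 0.5 quantile: PENG 5.4 h v AQLB 5.8 h. The all-patient median is the 0.5/(1 − p) quantile (0.625 and 0.526): PENG 7.2 h v AQLB 6.2 h. Sample medians reverse in about 27% of such trials.

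**The case against.** The strongest reply is that the plan never says it will drop rescue-free patients. Section 11.3 applies if data are missing, and a known non-event need not be missing. If 24 h is entered for these patients, Kruskal–Wallis ties them at the top rank. With a common cut-off and complete follow-up that is a valid rank test. In the first three Weibull scenarios it is 8 to 13 points below log-rank, and ANOVA 3 to 5 points. This stands: Kruskal–Wallis is not wrong in itself, and the large losses belong to the rescued-only reading. But the tied-rank rule is not written anywhere, and the only rule that is written points the other way.

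The size also rests on assumptions. The 29% ceiling is a mathematical limit, needing one identical dose among all users. Section 6.4 triggers rescue on pain either at rest or on movement, which may make rescue-free patients uncommon. Power at 27 evaluable per arm is lower than at 31, though the methods keep their order. The reversal example was built to reverse; even with two identical arms, 12.5% rescue-free each, the two handlings disagree on direction in about 19% of trials. These points limit what can be said about size. They do not remove the need for a rule, since the rate cannot be known in advance.

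**Conclusion.** The concern holds. Section 11.6 gives a censored outcome a method for fully observed values, and no section says what happens to patients without the event. With block arms 7.5–20% rescue-free, the rescued-only analysis loses roughly 23 to 47 points of power against log-rank (92 − 69 = 23; 80 − 33 = 47), and entering 24 h with Kruskal–Wallis loses about 8 to 13. These figures assume Weibull times and 31 per arm. If almost nobody is rescue-free, the handling of such patients hardly matters.

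This is a named secondary outcome. The primary outcome and the sample size are untouched. It should be fixed, but it does not threaten the trial's main conclusion.

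**What to change.** In Section 11.6, take this outcome out of the ANOVA/Kruskal–Wallis list and write:

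> Time from end of surgery to first rescue morphine will be analysed as time-to-event in the FAS, with patients who need no rescue censored at 24 h, or at last observation if earlier. Kaplan–Meier medians and the number rescue-free at 24 h will be reported per arm. Arms will be compared by log-rank test, with Bonferroni-adjusted pairwise log-rank tests.

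Cox hazard ratios may be added. In Section 11.3, state that needing no rescue within 24 h is not missing data. State in advance that time to first ambulation will be handled in the same way if any patient is discharged without walking. If the sponsor prefers to keep Kruskal–Wallis, the minimum is a written rule that rescue-free patients are tied at the top rank; this removes the selection but gave less power in the scenarios above.

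The cost is a change to Section 11.6 and a sentence in Section 11.3. No new data are needed, and SPSS runs Kaplan–Meier, log-rank and Cox. Section 11.8 describes interim analyses in the past tense; if the data have already been examined by arm, the change must be labelled post hoc.

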## **1. Background and Rationale**

Total hip arthroplasty (THA) is widely performed for traumatic hip fractures and degenerative hip disease in older adults and is associated with substantial postoperative pain that can delay mobilization and prolong hospital stay. Effective multimodal analgesia is essential to facilitate early rehabilitation and reduce opioid-related adverse effects in this vulnerable population.

Opioid analgesics provide rapid pain relief but carry important risks in elderly patients, including respiratory depression, delirium, constipation, nausea/vomiting, and prolonged hospitalization. Regional anesthesia techniques, particularly peripheral nerve and fascial plane blocks, are increasingly used as opioid-sparing strategies after THA.

The pericapsular nerve group (PENG) block targets the articular branches of the femoral, obturator, and accessory obturator nerves supplying the anterior hip capsule via local anesthetic injection between the psoas tendon and superior pubic ramus. It has been described as providing effective, largely motor-sparing postoperative analgesia for hip surgery and acute pain after hip fracture.

The anterior quadratus lumborum block (AQLB) deposits local anesthetic in the fascial plane between the quadratus lumborum and psoas major muscles, aiming to block lumbar plexus articular branches and provide analgesia for hip surgery. Previous studies reported favorable analgesic profiles of AQLB in THA.

Both PENG and AQLB appear anatomically capable of covering the operative field in THA, but they may differ in their balance between analgesic efficacy, opioid-sparing effect, and motor impairment. Comparative data between these two techniques in elderly

patients undergoing THA under general anesthesia are limited. This trial evaluates whether ultrasound-guided PENG block or AQLB offers superior postoperative analgesia and functional recovery compared with standard opioid-based analgesia and compares PENG and AQLB directly.

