## **11. Statistical Analysis Plan**

### **11.1 General Principles**

Statistical analyses will be performed using IBM SPSS Statistics (version 28). All randomized participants who receive the allocated intervention and have outcome data will be included in the primary analysis (modified intention-to-treat). Two-sided tests will be used with a significance level of  $P < 0.05$ . Continuous variables will be assessed for normality using the Shapiro–Wilk test and visual inspection of histograms and Q–Q plots. Normally distributed variables will be presented as mean  $\pm$  standard deviation and non-normally distributed variables as median (interquartile range). Categorical variables will be presented as counts and percentages. Adjustment for multiple pairwise comparisons will use Bonferroni correction where applicable.

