### **11.5 Primary Outcome Analysis**

The primary outcome, total morphine consumption in the first 24 postoperative hours, will initially be assessed for normality. If the distribution is non-normal, the primary analysis will use the Kruskal–Wallis test to compare the three groups. If the overall test is significant ( $P < 0.05$ ), pairwise comparisons between groups (PENG vs AQLB, PENG vs Control, AQLB vs Control) will be conducted using Mann–Whitney U tests with

Bonferroni-adjusted significance thresholds. Median differences and 95% confidence intervals will be reported when appropriate.

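### Adverse events and motor recovery are analysed by significance tests alone, with no between-arm estimate or interval, and at 31 per arm those tests usually miss small-to-moderate harms

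*Combined protocol and SAP*

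**What the plan says.** Section 2.2 lists motor recovery over 24 hours, and the incidence of block-related and morphine-related events, among the comparisons to be made. Section 1 makes motor function part of the rationale, saying of PENG and AQLB that "they may differ in their balance between analgesic efficacy, opioid-sparing effect, and motor impairment".

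Section 11.6 gives the analysis. For events: "Categorical outcomes, such as adverse event incidence and block failure rates, will be compared using chi-square or Fisher’s exact tests as appropriate". For strength and range of motion: "motor recovery scores will be analyzed at each time point using Kruskal–Wallis tests with Bonferroni-adjusted Mann–Whitney comparisons". It also allows exploratory mixed models of the time-by-group interaction, as an option.

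Section 11.1 sets the general rules: "Two-sided tests will be used with a significance level of" 0.05, categorical data shown as counts and percentages, and "Adjustment for multiple pairwise comparisons will use Bonferroni correction where applicable".

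Intervals for a between-arm difference appear once, in section 11.5, for morphine consumption: "Median differences and 95% confidence intervals will be reported when appropriate". Section 12 covers the recording and reporting of serious events, not their comparison between arms. Section 8 sizes the trial on opioid consumption only. No expected rate, SD, relevant difference or margin is given for any harm.

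**The concern.** A test can reject or fail to reject; it does not say how large a harm remains possible. If the power to detect a harm is low, a null result carries little information, and a p-value does not show that.

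The trial asks how the blocks balance analgesia against motor impairment and complications. The analgesic side gets an estimate and an interval. The harm side gets p-values and per-arm summaries. A reader of the results could not tell directly whether a non-significant comparison means no relevant harm or too few patients to know.

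**Working it through.** **1. What the sample was sized for.** Section 8: "a conservative standardized effect size of 0.35 was assumed" and "power of 80%, and three groups, the required sample size was 81 patients". Reading 0.35 as Cohen's f for a three-group ANOVA, the noncentrality is 81 × 0.35² = 9.92. Power at N = 81 is then 79.6%, and N = 82 is the first to reach 80%, so the stated figure is reproduced to within a patient or two. 81 × 1.15 = 93.15 gives 93, or 31 per arm. Nothing in this calculation concerns harms.

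**2. Adverse events, two arms.** Inputs: 31 per arm (section 8); two-sided 0.05, or 0.05/3 = 0.0167 with Bonferroni over three pairs (section 11.1). The event rates are assumptions. Power is the sum, over all pairs of counts (a, b), of Bin(a; 31, p₁) × Bin(b; 31, p₂) wherever the test's p-value is at or below alpha.

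| Assumed rates | Fisher, 0.05 | Chi-square, 0.05 | Fisher, 0.0167 | Chi-square, 0.0167 |
|---|---|---|---|---|
| 5% v 15% | 10% | 27% | 5% | 10% |
| 10% v 20% | 10% | 20% | 5% | 8% |
| 10% v 25% | 23% | 35% | 12% | 19% |
| 10% v 30% | 39% | 52% | 24% | 34% |
| 10% v 40% | 73% | 81% | 57% | 67% |

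Which column applies depends on expected counts. At 5% v 15% the expected count per arm is 31 × 0.10 = 3.1, so Fisher is the natural choice. At 10% v 30% it is 31 × 0.20 = 6.2, so chi-square normally applies. If attrition leaves 27 per arm, 10% v 25% falls to 17% (Fisher) or 33% (chi-square) at 0.05.

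**3. Adverse events, three-arm chi-square at 0.05 (simulated, 31 per arm).** 5/5/15%: 25%. 10/10/25%: 37%. 10/10/30%: 56%. 10/10/40%: about 87%.

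**4. Motor scores.** Assumptions: normal data, one time point, the same loss in both blocks against Control. Kruskal–Wallis at 0.05 is followed by Mann–Whitney at 0.0167 (simulated, 31 per arm).

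- Loss of 0.5 SD: omnibus power about 48%; block-v-Control power about 29% if gated on the omnibus test.
- Loss of 0.7 SD: omnibus about 78%; pairwise about 59%.

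**5. What an interval would show.** Newcombe's interval for p₁ − p₂ uses the Wilson limits (l, u) of each arm. With d = p₁ − p₂:

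- lower = d − √[(p₁ − l₁)² + (u₂ − p₂)²]
- upper = d + √[(u₁ − p₁)² + (p₂ − l₂)²]

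Take 8/31 v 3/31. Here p₁ = 0.2581 (Wilson 0.1370 to 0.4325), p₂ = 0.0968 (0.0335 to 0.2490) and d = 0.1613.

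- lower = 0.1613 − √(0.1211² + 0.1522²) = 0.1613 − 0.1945 = −0.033
- upper = 0.1613 + √(0.1744² + 0.0633²) = 0.1613 + 0.1855 = +0.347

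Fisher p = 0.18, with an interval of −3 to +35 points.

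For 3/31 v 3/31, d = 0 and the limits are ±√(0.1522² + 0.0633²), or ±16.5 points. For 6/31 v 3/31, Fisher p = 0.47 and the interval is −8.6 to +27.7 points. With no events in an arm, the exact two-sided 95% upper limit is 1 − 0.025^(1/31) = 11.2%.

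**The case against.** **The plan draws no safety conclusion.** A reader might infer that null results will be reported as equal safety or as motor sparing. The documents do not say so. Motor sparing appears only in section 1, as a description of earlier reports on PENG, and no margin or decision rule is attached to these secondary outcomes. The misreading is a risk the plan leaves open, not something it commits to.

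**The tests do not miss every relevant harm.** A reader might also infer that they miss any important harm most of the time. That depends on a size the documents do not define. A tripling from 10% to 30% is close to an even chance with chi-square (52%), a tripling from 15% to 45% is found about 76% of the time, and 10% v 40% is found in 73–81% of trials. The listed events include nausea, vomiting and hypotension, which need not be rare. For motor scores no SD is given, and a loss of 0.7 SD or more is usually found by the omnibus test. The gate used for the pairwise motor figures is stated in section 11.5 for the primary outcome; section 11.6 does not repeat it.

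**Counts and percentages will be shown.** True, and a reader could compute an event interval from them. But this leaves the estimate to the reader. It does not work for motor scores summarised as medians, and the optional mixed models commit to no interval.

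**Intervals will not settle safety without a margin.** Also true. They show what remains possible; they do not deliver a verdict. Unadjusted intervals over several pairs and time points also need a label, given the Bonferroni rule in section 11.1.

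These points narrow the claim to small-to-moderate harms and to a risk of misreading. None supplies the missing estimates.

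**Conclusion.** The concern holds in this limited form. Section 11.6 commits to no between-arm estimate or interval for adverse events or motor recovery, while section 11.5 plans them for the primary outcome. That follows from the text alone.

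The size rests on assumed rates and SDs. Event differences of 10 to 15 points from a 5–10% base are missed more often than found under every test tried. At 20 points (10% v 30%) detection at 0.05 ranges from 39% to 56% by test, and at 30 points it is likely. A 0.5-SD motor loss is about an even chance for the omnibus test and is usually missed pairwise. A non-significant event comparison can leave an excess of roughly 15 to 35 points unexcluded, and the planned output would not show it. This is a cheap improvement to reporting; it does not affect the primary analysis.

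**What to change.** In section 11.6:

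- For each adverse event, report the pairwise risk difference with a 95% Newcombe interval.
- Compare block-related complications between PENG and AQLB only, because Control receives no block (section 6.2.3). Give an exact upper bound when an arm has zero events.
- For the motor measures already collected, report the pairwise difference with a 95% interval: a mean or Hodges–Lehmann difference in degrees for active hip flexion, and a rank-based effect such as the Mann–Whitney probability for manual muscle test grades. No new endpoint is needed.
- Report these whether or not the omnibus test is significant, keep p-values as secondary, and label the intervals as unadjusted for multiplicity.
- Add: *A non-significant difference will not be reported as evidence of equal safety or of motor sparing; the harm-side limit of the interval will be stated.*

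The cost is SAP wording and a few table columns, with no new patients or data. The intervals will be wide, and safety statements will have to be more cautious.
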